5.3 Primary outcomes measures

The primary clinical effectiveness endpoint is a composite event-free survival time examined over the trial duration (36 months) comprising:

- Acute limb ischaemia
- Major lower limb amputation
- Myocardial infarction

- Ischaemic stroke
- All-cause mortality

The primary safety outcome is the International Society for Thrombosis and Haemostasis (ISTH) defined major- or clinically relevant non-major bleeding*.

*Clinically relevant non-major bleeding is bleeding that results in hospitalisation, medical or surgical intervention for bleeding, an unscheduled clinical visit, or a change in antithrombotic therapy (24).

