14.2 Blinding

The CLARITY trial does not use blinding of patients or clinicians. The statistician will perform the primary analysis blind to allocation.

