14.3 Sample size

We aim to recruit 1239 participants over 36 months and follow them up for a maximum of 36 months if recruited earlier in the trial, or a minimum of 12 months if recruited later. Assuming a 12-month event-free survival rate of 65.0% in the clopidogrel alone arm; an increase to 75.6% in at least one of the intervention arms, corresponding to a hazard ratio of 0.65 (10,11,14,35), a dropout/loss to follow-up rate of 8%/year (unpublished BASIL 3 data); a two-group log-rank test of equal exponential survival with a two-sided alpha of 2.5% (accounting for the three-arm design) and 90% power requires 387 primary outcome events (157 expected in the clopidogrel alone arm, 115 in each of the combination arms) to be observed (BASIL 3 data provided by Chief Investigator). Given the 36-month recruitment period (assuming 25%, 35% and 40% recruitment in the first, second and third year, respectively) and a maximum follow-up period of 36 months, this translates into 413 participants per arm, or 1239 in total (calculated with ART version 1.1.0 using Stata version 17.0) (36,37).

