- Remaining intercurrent events: Death is incorporated into the clinical effectiveness primary outcome. Treatment discontinuation is covered by the previous attribute.
- Population-level summary: Hazard ratios, including fixed effects for allocation and random
 effects to model heterogeneity between sites. Regression analysis results will be presented as
 point estimates with confidence intervals and p-values from a log-rank test, and Kaplan-Meier
 curves of cumulative event rates at 36 months (31,32) will be generated to compare arms over
 time.

The primary safety outcome analysis will also use a two-level Cox regression as described above but include only those participants who received at least one dose of their allocated medication ('ontreatment' population). This analysis will include safety events that occurred after receiving the first dose of the trial medication and within 5 days after receiving the last dose.

Secondary outcomes will also be analysed based on ITT (for effectiveness outcomes) or 'on- treatment' populations (for safety outcomes) and using appropriate two-level regression models depending on the type of outcome: Cox regression for time-to-event outcomes, linear regression for continuous outcomes such as QoL measures (allowing for repeated measures where appropriate), and logistic regression for binary outcomes such as reintervention rates.

Table 7. Planned outcome analysis

Outcome	Measure	Analysis	Time frame	
Composite primary	Acute limb ischaemia	Two-level Cox regression		
outcome - Composite event-	Major lower limb amputation	Two-level Cox regression	2m, 6m, 12m,	
free survival time of the following:	Myocardial infarction	Two-level Cox regression	24m and 36m	
the following:	Ischaemic stroke	Two-level Cox regression		

Outcome	Measure	Analysis	Time frame		
	All-cause mortality	Two-level Cox regression			
Primary safety outcome	Major bleeding (ISTH definition)	Two-level Cox regression	2m, 6m, 12m, 24m and 36m		
	MALE (defined as amputation or any major reintervention)	Two-level Cox regression	2m, 6m, 12m, 24m and 36m		
	MACE (defined as recurrent CLTI, amputation affecting contralateral limb, acute coronary syndrome, ischaemic stroke)	Two-level Cox regression			
Caracilar	Major bleeding (BARC definition)	Two-level Cox regression			
Secondary outcomes	Major bleeding (TIMI definition)	Two-level Cox regression			
	Minor bleeding	Two-level Cox regression			
	Primary patency of artery	Two-level logistic regression			

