	Secondary patency of artery	Two-level logistic regression			
	Reintervention	Two-level logistic regression			
	Healing of tissue loss	Two-level logistic regression			
	VascuQoL-6	Two-level linear regression	Baseline, 2m, 6m,		
	EQ-5D-5L	Two-level linear regression	12m, 24m and 36m		
	MALE using other major definitions	Two-level Cox regression	2m, 6m, 12m,		
Tertiary outcomes	MACE using other major definitions	Two-level Cox regression	- 24m and 36m		
	Complications from trial medications	Two-level logistic regression	Baseline, 2m, 6m, 12m, 24m and 36m		

The components of the composite primary outcome will also be analysed individually; for this, we will use competing risk models with all-cause mortality being a competing risk for other non-fatal outcomes. We will also explore the use of recurrent event models to reflect that patients may experience more than one outcome event and/or the same event multiple times (38,39). The distribution of different types of events over time will be visualised using e.g. swimmer plots.

In additional secondary analyses, we will calculate win statistics such as the win ratio or win odds to more directly express the probability of one treatment being better than the other, or being the best (40,41). We will also estimate and compare proportions of primary outcome events (as a composite and also each component individually) at 12 and 24 months, respectively.

We will consider the impact of different types of intercurrent events such as the timing of starting trial medication, discontinuing the prescribed medication, crossing over between arms, or using non-trial medication. To this end, sensitivity analyses will be performed using the 'on-treatment' population (for effectiveness outcomes) as well as other meaningful analysis populations e.g., based on the medication actually received ('as-treated') or including only those who fully adhered to their allocated

regimen ('per-protocol'). These will be specified in detail in the SAP using the estimands framework (40). Additional adjusted analysis incorporating important covariates, as well as potential subgroup analyses, will be specified in the SAP with stakeholder and PPI input (41). Variables likely to be considered include arterial territory (such as femoropopliteal or tibial), devices used during the intervention such as drug-eluting technology and diabetes.

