If key assumptions such as proportional hazards do not hold, we will try alternatives such as accelerated failure time models or adding a stratification variable or time-varying covariate. To assess potentially informative censoring and non-compliance, an inverse probability-of-censoring weighted analysis will be undertaken.

A comprehensive SAP will be finalised by the trial statistician, with support from the TMG, agreed by the TSC, and signed off prior to any analysis being conducted. Results will be reported in line with the Consolidated Standards of Reporting Trials (CONSORT) statement and its extensions to multi-arm (42) and adaptive designs (43).

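### Bleeding is analysed on treatment only: Section 15.1 names no supporting analysis of all randomised participants by allocated arm

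*Protocol*

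**What the plan says.** Section 5.3 defines the primary safety outcome as ISTH major or clinically relevant non-major bleeding. Section 15.1 analyses it with a two-level Cox model that will "include only those participants who received at least one dose of their allocated medication". Events count from the first dose and "within 5 days after receiving the last dose". Secondary outcomes are split the same way: ITT for effectiveness, and on-treatment "populations (for safety outcomes) and using appropriate two-level regression models".

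The primary effectiveness analysis takes all randomised participants with non-zero follow-up, and its estimand applies whether or not the regimen was started or stopped. The base-case economic analysis (15.3) is also ITT.

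For robustness, 15.1 says that "sensitivity analyses will be performed using the 'on-treatment' population (for effectiveness outcomes", adds as-treated and per-protocol sets as examples of other possible populations, and leaves the detail to the SAP. It also says that an "inverse probability-of-censoring weighted analysis will be undertaken" to assess informative censoring and non-compliance; no outcome is named there. Section 14.7 only points back to 15.1.

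On blinding, Section 14.2 states: "The CLARITY trial does not use blinding of patients or clinicians".

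**The concern.** Randomisation makes the arms comparable when everyone randomised is compared by allocated arm. The safety set departs from this in two ways: it removes people who never took their allocated drug, and it stops counting 5 days after the last dose. In an open-label trial both can depend on the arm. A clinician or patient worried about bleeding may not start, or may stop, a combination but continue single-agent clopidogrel. If those who leave the combination arms have above-average bleeding risk, those who remain have below-average risk and the combination looks safer than it is. If the low-risk ones leave, it looks more harmful.

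The trial is meant to weigh fewer ischaemic events against more bleeding. As written, the two can be set side by side in the on-treatment set, because on-treatment effectiveness is planned. Non-fatal bleeding has no named estimate in the randomised set on which the primary effectiveness result rests.

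**Working it through.** **Which analyses could apply to bleeding**

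| Analysis in 15.1 | Open to bleeding? | All randomised, by allocated arm? |
|---|---|---|
| On-treatment (primary and secondary safety) | Yes | No |
| As-treated | Not excluded | No: grouped by drug received |
| Per-protocol | Not excluded | No: full adherers only |
| Inverse-probability-weighted | Not excluded | Not stated; relies on a model for censoring |
| ITT | Assigned to effectiveness | Yes |

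**What the window leaves out.** It leaves out bleeds in non-starters, bleeds between randomisation and first dose, and bleeds more than 5 days after stopping. It does not leave out the bleed that causes the stop: under 5.3 bleeding that results in "an unscheduled clinical visit, or a change in antithrombotic therapy" is itself an event.

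**Follow-up time.** The protocol gives no figure for the safety analysis, so there is none to reproduce. Inputs from the protocol: accrual ("assuming 25%, 35% and 40% recruitment in the first, second and third year, respectively"), follow-up of 12 to 36 months with close at 48 months, and 8%/year dropout.

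- With uniform entry within each year, mean administrative follow-up is 36, 30 and 18 months for the three yearly cohorts: 0.25×36 + 0.35×30 + 0.40×18 = 26.7 months.
- Dropout hazard d = −ln(0.92) = 0.0834/year. Averaging (1 − e^(−d·f))/d over follow-up times f gives 24.2 months, before deaths.
- Let C(t) be the probability of still being followed at t, and h = −ln(1 − r) for an assumed permanent stopping rate r. The share of time more than 5 days after stopping is 1 − ∫C(t)·e^(−h·max(t − 5 days, 0))dt / ∫C(t)dt. For r = 5%, 10% and 20% a year this is 5.7%, 11.1% and 21.5%.

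**Illustration of bias.** All inputs here are assumed except accrual, follow-up and dropout. The low-risk bleeding hazard is 0.05/year; 30% of participants are high-risk at k = 2 or 3 times that; after stopping, the hazard is the clopidogrel rate. In the clopidogrel arm 2% do not start and 10%/year stop, except in E. The hazard ratio (HR) solves the expected Cox score equation: the sum over time of e₁ − (e₀ + e₁)·Y₁θ/(Y₀ + Y₁θ) equals 0, where e and Y are expected events and numbers at risk in each arm (1 = combination, 0 = clopidogrel).

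Combination arm (non-start, stop per year):
- A: as clopidogrel.
- B: 5%, 20%, unrelated to risk.
- C: low-risk 2%, 12%; high-risk 12%, 35%.
- D: low-risk 6%, 25%; high-risk 2%, 10%.
- E: 1%, 3% in both arms, except high-risk combination 2%, 6%.

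| Scenario | True HR 1.00: on-treatment (k=2/3) | ITT | True HR 1.50: on-treatment | ITT |
|---|---|---|---|---|
| A | 1.00/1.00 | 1.00 | 1.49/1.48 | 1.43/1.42 |
| B | 1.00/1.00 | 1.00 | 1.49/1.48 | 1.37/1.36 |
| C | 0.94/0.91 | 1.00 | 1.41/1.35 | 1.36/1.34 |
| D | 1.04/1.06 | 1.00 | 1.55/1.57 | 1.38/1.38 |
| E | 0.99/0.99 | 1.00 | 1.48/1.46 | 1.46/1.45 |

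On-treatment values slightly below 1.50 in A and B reflect earlier depletion of high-risk participants in the combination arm, not selective stopping.

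**The case against.** The strongest reply is that on-treatment safety analysis is standard, that 15.1 leaves further populations to a SAP not seen here, and that its list is open. The SAP may therefore contain an ITT bleeding analysis. This stands, and it limits the point to what the protocol names. But the protocol itself chose the safety population and the window, and each alternative set it names moves away from ITT.

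A reader might infer that no planned analysis of bleeding could reveal selective stopping. The text does not support that: the as-treated, per-protocol and weighted analyses are not confined to effectiveness, and the weighted analysis is aimed at informative censoring. None of them is stated as a comparison of all randomised participants by allocated arm.

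Nor is harm absent from the randomised set. Fatal bleeds enter the ITT composite through all-cause mortality, and the ITT economic analysis picks up consequences of bleeding through quality of life and resource use. Non-fatal bleeding as a clinical outcome is what has no named estimate there.

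Finally, ITT is not the better measure of drug harm. At a true HR of 1.50 the on-treatment value is closer to 1.50 in every scenario above, and an ITT count from randomisation includes bleeds before the first dose, which can come up to 10 days after the procedure. These are reasons to keep on-treatment as primary, not reasons to omit the other analysis.

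**Conclusion.** The point holds as a cheap improvement, not as an error. Section 15.1 fixes an on-treatment set for primary and secondary bleeding and names no all-randomised bleeding analysis beside it. In an open-label trial that leaves no named bleeding comparison fully protected by randomisation.

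Neither the direction nor the size of any bias can be determined from the protocol. With no true difference, the illustration gives on-treatment hazard ratios of 0.91 to 1.06, and the extremes need strongly risk-dependent stopping (35% against 12% a year in scenario C). If stopping is rare or unrelated to risk, the result is 0.99 to 1.00. The 6% to 21% of uncounted follow-up time rests on assumed stopping rates and ignores deaths, so it is probably somewhat high.

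**What to change.** Keep the on-treatment analysis as primary. Add to 15.1 and Table 7 a supporting ITT analysis of ISTH major or clinically relevant non-major bleeding: all randomised participants with non-zero follow-up, by allocated arm, from randomisation to end of follow-up. State that the censoring at a change of medication in 11.4 does not apply to it; otherwise it would be cut short as well. Report it beside the on-treatment result, with numbers and reasons for non-starting and stopping by arm.

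The cost is one extra model and some wording. Bleeding is already collected at each follow-up (12.2), drug start and changes with reasons are recorded (11.12.1, 12.2.1), and stopping medication is kept separate from leaving follow-up (10.1).

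The downside is dilution: if 20% of combination-arm time (assumed) is off treatment at the clopidogrel rate, a hazard ratio of 1.50 becomes 0.8×1.5 + 0.2×1.0 = 1.40. Bleeds before the first dose are also included. The ITT result therefore supports the on-treatment one and does not replace it.

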15.1.1 Sub-group & interim analysis

A planned interim analysis of the co-primary outcomes will be conducted when 60% of the planned maximum number of primary outcome events have been observed. The interim analysis will compare each of the combination arms against the clopidogrel-only arm (which has the lowest predicted clinical effectiveness) using futility-stopping criteria based on conditional or predictive power which leads to minimal overall power loss. These criteria will be finalised during the trial set-up phase and fully specified in the SAP.

If the futility of the clopidogrel-only arm is shown in at least one of the two comparisons, the trial will continue with the two combination arms only. Participants in the futile arm will continue with the allocated drug and will be followed up until the end of the trial. If all three arms continue through to the final analysis, each of the combination arms will be compared to clopidogrel only, each at 2.5% alpha. If only one is significantly better, it will be declared the most effective. If both combination therapy arms are significantly better, they will then be compared against each other using the full 5% alpha, thus ensuring strong control of the familywise type I error rate.

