6.1 Design

We will conduct a pragmatic, adaptive, multicentre, open-label, three-arm RCT, with internal pilot and adaptive interim analysis to examine the futility of the arm with the lowest predicted clinical effectiveness. The trial will evaluate the clinical and cost-effectiveness of three commonly used antithrombotic regimens following endovascular intervention for CLTI: once daily 75mg clopidogrel alone; once daily 75mg aspirin plus once daily 75mg clopidogrel; and once daily 75mg aspirin plus twice daily 2.5mg low-dose rivaroxaban. We plan to enrol 1,239 participants. This is a Type A Clinical Trial of Investigational Medicinal Product (CTIMP) as all 3 arms include only medicinal products within the licensed range of indications, dosage and form, and which are already given in routine clinical practice. We expect to reach the enrolment target within 36 months of starting recruitment. The study

will end 6 months after the date of the last data capture. Data collection will involve recording health outcomes, patient-reported outcome measures (PROMs) and serious adverse events in the electronic case report form (CRF) as well as questionnaires administered via telephone, videocall, email and post.

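### The interim rule in Section 15.1.1 can close only clopidogrel, the reference arm, without saying what its futility means or what is tested against it afterwards

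*Protocol*

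**What the plan says.** Protocol Section 6.1 describes an interim analysis "to examine the futility of the arm with the lowest predicted clinical effectiveness". Section 15.1.1 identifies that arm as clopidogrel alone and sets the look at 60% of the planned maximum number of primary events. The criteria are to rest on conditional or predictive power, with thresholds left to the SAP, and are meant to cost little power overall.

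The action is fixed in the protocol itself: "If the futility of the clopidogrel-only arm is shown in at least one of the two comparisons", the trial goes on with the two combinations. Participants already on clopidogrel stay on it and are followed to the end. Sections 9.5.2 and 14.1 say only that one arm may be dropped and allocation then becomes 1:1. No section gives a rule for dropping a combination.

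On the final tests: "If all three arms continue through to the final analysis, each of the combination arms will be compared to clopidogrel only", each at 2.5%, with the two combinations compared at 5% if both succeed. No test or alpha is stated for a trial that continues with two arms. Section 15.1 keeps all randomised participants with non-zero follow-up in the primary Cox model, and its estimand names all three regimens.

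Clopidogrel is also the reference in Section 14.3: "Assuming a 12-month event-free survival rate of 65.0% in the clopidogrel alone arm", and "an increase to 75.6% in at least one of the intervention arms, corresponding to a hazard ratio of 0.65".

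**The concern.** Conditional-power futility normally means that an experimental arm is unlikely to beat its reference, and the arm to stop is then the experimental one. Here the same finding would remove the reference. A combination doing no better than clopidogrel would lead to the closure of clopidogrel and continued recruitment to that combination.

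The threshold can properly wait for the SAP. The arm removed, the one-of-two trigger and the condition on the final tests are protocol text, and an SAP threshold does not repair them.

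At stake is the primary question. After a closure, the only comparison left by implication is one combination against the other. Under the planning events ("157 expected in the clopidogrel alone arm, 115 in each of the combination arms") both combinations have a hazard ratio of 0.65, so that comparison has no difference to find.

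**Working it through.** **Inputs.** Section 14.3: "a two-sided alpha of 2.5% (accounting for the three-arm design) and 90% power requires 387 primary outcome events", split 157/115/115; hazard ratio 0.65; "a dropout/loss to follow-up rate of 8%/year"; accrual 25/35/40% over three years. Section 15.1.1: interim at 60% of events. Assumed, because the protocol gives no value: thresholds of 10% and 20%.

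**The plan's own figure.** Schoenfeld: 4(2.2414 + 1.2816)² / (ln 0.65)² = 49.65 / 0.1856 = 268 events per pair. Freedman: 12.41 × (1.65/0.35)² = 276. Stated: 157 + 115 = 272. Power with the unequal split: Φ(0.4308 × √(157 × 115/272) − 2.2414) = Φ(1.27) = 0.90. Exponential survival with a data cut 36 months after recruitment starts gives 157/114/114 events. The figure reproduces.

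**Interim.** 0.60 × 387 = 232 events. This falls at about month 25 with 63% recruited if the arms are equal, and at about month 28 with 72% recruited if both combinations have hazard ratio 0.65.

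**Conditional power.** With information fraction t = 0.6, final critical value 2.2414 and interim statistic z (positive favours the combination):

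- current trend: Φ((z/√t − 2.2414)/√(1−t))
- design effect: Φ((z√t + θ(1−t) − 2.2414)/√(1−t)), where θ is the expected final z at hazard ratio 0.65

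**Worked case: equal arms, 77.4 events each, 20% threshold.** The standard error of the log hazard ratio is √(2/77.4) = 0.161, and θ = 3.46.

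- Current trend: below 20% when z < 0.775 × (2.2414 − 0.632 × 0.842) = 1.32, an observed hazard ratio above 0.81. The chance is 91% for one comparison and 97% for at least one of two (correlation 0.5).
- Design effect: below 20% when z < (1.709 − 0.4 × 3.46)/0.775 = 0.42, an observed hazard ratio above 0.94. The chance of at least one is 81%.

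**Probability that clopidogrel is closed** (simulated, 3 million runs; ranges cover the 10% and 20% thresholds, or 90% and 80% in the last column):

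| True hazard ratios | Interim events (clopidogrel / combinations) | Combination unlikely to win, design effect | Same, current trend | Combination clearly winning, current trend |
|---|---|---|---|---|
| 1.0, 1.0 | 77 / 77, 77 | 69–81% | 95–97% | 2–3% |
| 0.65, 1.0 | 86 / 61, 86 | 49–63% | 87–91% | 58–66% |
| 0.65, 0.65 | 96 / 68, 68 | 1–2% | 10–14% | 81–87% |

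On the usual reading the rule runs backwards: clopidogrel is closed most often when it is as good as the combinations and least often when both beat it. A third reading, low conditional power that clopidogrel beats a combination, is met in 95–97% of trials under equality and nearly 100% when at least one combination works, so it does not discriminate.

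**Power.** With hazard ratios 0.65 and 1.0 and no interim closure, at least one test against clopidogrel is significant in 86% of trials (90% with the planned 272 events per pair). On the usual reading with design-effect conditional power, the chance of both keeping that test and reaching significance is 47% at the 10% threshold and 35% at 20% (46% and 33% with 272 events per pair).

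The fraction 0.60 is taken as Section 15.1.1 states it, relative to 387 events.

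**The case against.** The sponsor's best answer is that clopidogrel is examined because it is the expected loser, so its futility means that it can no longer be the best arm. One comparison is then a logical trigger, since an arm clearly beaten once cannot be best. The wording about lowest predicted effectiveness and little power loss fits this reading better than the usual one. This stands as a plausible intention, and equal arms would then rarely close clopidogrel: about 2–3% on the current trend, 3–7% with the design effect at the same cut-offs. But the protocol does not say so, and on this reading the rule is an efficacy decision without a boundary.

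A reader might infer that the trial would generally discard its primary question whenever the arms are equal. The documents do not support that, because the result depends on the undefined direction. A reader might also infer that no comparison with clopidogrel survives a closure. That is too strong as well: Section 15.1.1 follows the closed arm to the end, and Section 15.1 keeps all three regimens in the primary model. What is missing is a stated confirmatory test and its alpha.

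Nor is closure automatic in practice. The IDMC recommends and the TSC decides (Sections 22.3 and 22.4). Those committees still need a rule with one meaning.

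**Conclusion.** Section 15.1.1 is wrong as written and should be corrected before the interim. It fixes that only the reference arm can close and that one comparison suffices, but leaves the direction of futility open. Under equal arms the closure probability runs from about 2% to 97% depending on the reading. On the usual reading it is 69–97% with equal arms and 49–91% with hazard ratios 0.65 and 1.0, which contradicts the stated aim of little power loss. On the favourable reading the problem is an unlabelled superiority decision without a boundary. On either reading, no confirmatory test or alpha against clopidogrel is stated after a closure, and Sections 15.1 and 15.1.1 need reconciling on this.

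The percentages rest on assumed thresholds of 10–20% (80–90% for the winning reading), exponential survival and 60% information. The defects of wording do not depend on them.

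**What to change.** Rewrite Section 15.1.1 before the interim:

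1. Low conditional power that a combination beats clopidogrel never closes the clopidogrel arm. Any futility action on that basis applies, non-binding, to the combination concerned.
2. If clopidogrel may be closed early, call this an efficacy decision and set a superiority boundary in advance. The level, and whether one or both comparisons must cross it, is the sponsor's choice. If crossing itself supports a claim, its alpha comes out of that comparison's 2.5%.
3. On every path, keep the final tests of each combination against clopidogrel at 2.5% each, and state where the combination-versus-combination test stands after a closure. Use participants randomised while clopidogrel was open, or stratify by before and after closure. Under the planning accrual about 28–37% of the 1,239 would be randomised after a closure at the interim, all to combinations and without concurrent clopidogrel controls.

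Align Sections 6.1, 9.5.2, 14.1 and 15.1. The cost is protocol and SAP wording, with no extra participants. The downsides are that clopidogrel can no longer be closed on weak evidence, and that after a closure the comparison with it uses fewer combination participants.

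### Section 15.1.1 declares a combination the most effective when only it beats clopidogrel, although the two combinations have not been compared

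*Protocol*

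**What the plan says.** Section 15.1.1 of the protocol fixes the final decision rule itself; only the futility criteria are left to the SAP. "If all three arms continue through to the final analysis, each of the combination arms will be compared to clopidogrel only, each at 2.5% alpha". Two branches follow:

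- One combination significant: "If only one is significantly better, it will be declared the most effective".
- Both significant: "If both combination therapy arms are significantly better, they will then be compared against each other using the full 5% alpha".

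The section closes with the statement that this is "thus ensuring strong control of the familywise type I error rate".

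No other section adds a direct comparison in the first branch. Section 15.1 mentions win statistics that bear on which treatment is best, but as additional secondary analyses that do not govern the declaration.

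Section 14.3 gives the design figures: two-sided alpha of 2.5% per comparison, hazard ratio 0.65, and "90% power requires 387 primary outcome events", with "157 expected in the clopidogrel alone arm, 115 in each of the combination arms".

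**The concern.** Calling a regimen the most effective of three is a claim about both other arms. In the first branch the claim over clopidogrel has a test behind it. The claim over the other combination has none. A combination with p = 0.02 against clopidogrel would be placed above one with p = 0.03, although such results say almost nothing about how the two differ. The direct comparison is run where both win and omitted in the one branch where a ranking is announced without it.

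The familywise statement holds for the three tests that the section describes. It does not reach the ranking in the first branch, because that ranking is not the result of any of them.

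The stakes are practical. Section 5 says that the trial should give definitive evidence for policy makers. Section 4.1 puts rivaroxaban 2.5 mg at £1.80 a day and clopidogrel at £0.05 a day. An unsupported ranking could steer prescribing between two equally effective regimens of very different price.

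**Working it through.** **Inputs (section 14.3).** Hazard ratio (HR) 0.65; two-sided alpha 2.5%, critical value 2.2414; 157 clopidogrel events and 115 per combination, so 157 + 115 = 272 per comparison.

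**The plan's own figures.** ln(0.756)/ln(0.65) = 0.649, which matches the stated HR. Events for 90% power by Schoenfeld's formula: 4 × (1.2816 + 2.2414)² / (ln 0.65)² = 268; Freedman's formula gives 276. The stated 272 lies between them. Power with 272 events: |ln 0.65| × √(272/4) = 3.552, and Φ(3.552 − 2.2414) = 0.905. With the 157/115 split: 0.4308/√(1/157 + 1/115) = 3.510, and Φ(3.510 − 2.2414) = 0.898. The stated 90% is reproduced.

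**Chance that exactly one combination is significant when the two are equal.** The two z-statistics share the clopidogrel arm, so they are correlated: ρ = (1/157)/(1/157 + 1/115) = 0.42 with the planned split, or 0.5 if events are taken as equal across arms. Then

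P(exactly one) = 2 × [power − P(both significant)],

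with P(both) from the bivariate normal distribution. For HRs other than 0.65, clopidogrel stays at 157 events and the combination count is scaled under the same exponential, accrual and dropout assumptions. The last column keeps 272 events and ρ = 0.5.

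| Shared HR | Events per combination | Power per comparison | P(both) | P(exactly one) | P(exactly one), 272 events, ρ = 0.5 |
|---|---|---|---|---|---|
| 0.65 | 115 | 0.898 | 0.824 | 0.147 | 0.130 |
| 0.70 | 121 | 0.760 | 0.626 | 0.270 | 0.255 |
| 0.75 | 128 | 0.568 | 0.395 | 0.346 | 0.330 |
| 0.76 | 129 | 0.527 | 0.352 | 0.350 | 0.333 |
| 0.80 | 134 | 0.365 | 0.202 | 0.326 | 0.305 |

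The peak comes where power per comparison is about 50%. Near it, about 0.31 of the 0.35 are trials in which a direct comparison of the combinations would not reach 5%. At HR 0.65 it is 0.124 of 0.148 (simulated).

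**More events.** Section 15.1 places the final analysis 48 months after recruitment starts. If follow-up to that point yields about 229 clopidogrel events (an assumption; section 14.3 states 157), patient-level simulation gives 0.03 at HR 0.65, 0.26 at 0.75 and a peak of 0.34 at 0.80. The peak moves but does not vanish.

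**Interim analysis.** The table does not model dropping clopidogrel. The futility criteria are not in the protocol, so I assumed that clopidogrel is dropped when current-trend conditional power in either comparison exceeds a threshold between 80% and 99%. The share over all trials is then 0.16 to 0.28 at HR 0.77 and 0.05 to 0.10 at HR 0.65. Among trials that continue with three arms it is 0.31 to 0.36 and 0.27 to 0.36, because those that continue are the ones with less clear interim results.

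**With a direct test required.** Total false ranking, including false rejection in the both-significant branch:

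| Shared HR | Rule as written | Direct test at 5% also required |
|---|---|---|
| 0.65 | 0.173 | 0.050 |
| 0.75 | 0.352 | 0.047 |
| 0.76 | 0.355 | 0.047 |

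**Familywise error of the corrected rule.** Let the direct test at 5% open once at least one comparison with clopidogrel is rejected.

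- All three arms equal: an error needs a false rejection against clopidogrel first, with probability at most 2.5% + 2.5% = 5%.
- At least one of the three equalities false: at most one of the other two can be true, since two true equalities would force the third. That one is tested at 2.5% or 5%.

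The familywise error is therefore at most 5% in every case.

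**The case against.** The tests against clopidogrel are sound. A fixed split of 2.5% and 2.5% is a valid Bonferroni procedure, it matches the sample size calculation, and the gated direct comparison controls the familywise error for the three tests named. The declaration will also not be read alone: hazard ratios with confidence intervals, win statistics, the bleeding outcome and cost per QALY will stand beside it. All of this is right, but none of it supplies a test for the ranking or changes the label that the protocol attaches to the single winner.

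Three stronger readings are tempting and not supported:

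- That a third of all trials would end in a false ranking. That figure is a maximum over effect sizes. It requires equal combinations at a shared HR near 0.76, where each comparison has only about 50% power, and it applies only when all three arms reach the final analysis. At the protocol's own HR it is 13-15%.
- That the familywise statement is simply false. It is true of the tests described; the untested ranking lies outside it.
- That the fixed alpha split is part of the error and Holm's method is needed. Holm would add power, but it leaves the fault in place: at HR 0.75 with 272 events it lowers the exactly-one result from 33% to 22%, and those trials would still produce an untested ranking.

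**Conclusion.** The sentence is wrong as written and should be changed before any analysis, because it governs the trial's main conclusion. When the two combinations are truly equal and all three arms reach the final analysis, it ranks one above the other through this branch in about 13-15% of trials at HR 0.65 with 272 events per comparison, and in at most about 33-35%, near HR 0.76. The size rests on proportional hazards, the event counts in section 14.3 and no dropping of clopidogrel at the interim. If dropping is possible, the share over all trials is lower, by an amount that depends on criteria the protocol does not fix. The logical fault depends on none of these figures.

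**What to change.** In section 15.1.1, replace the sentence on a single significant combination with: *If only one combination is significantly better than clopidogrel, it is declared superior to clopidogrel; it is declared the most effective only if the direct comparison with the other combination is also significant at two-sided 5%.* State that the direct comparison may be tested once at least one comparison with clopidogrel has been rejected, and that its hazard ratio and confidence interval are reported in every branch. The familywise statement can then stay and will cover the ranking.

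The cost is wording in the protocol and SAP and one further contrast from the Cox model already planned. Sample size, data collection and the two tests against clopidogrel do not change. Holm's method for those two tests is an optional gain in power and is not needed for this correction.
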